6.3. Dosage and administration of study vaccines/product

Table 12 Dosage and administration

Type of contact and timepoint	Dose to be administered	Study Group	Treatment name	Route ¹	Site	Side
Visit 2	100000 IU	Coad group	Vitamin A	O	Not applicable	Not applicable
	0.5 ml	Coad group	RTS,S/AS01 _E	IM	Deltoid	Left
	100000 IU	RTS,S group	Vitamin A	O	Not applicable	Not applicable
	0.5 ml	RTS,S group	RTS,S/AS01 _E	IM	Deltoid	Left
	100000 IU	Control group	Vitamin A	O	Not applicable	Not applicable
Visit 3	0.5 ml	Coad group	RTS,S/AS01 _E	IM	Deltoid	Left
	0.5 ml	RTS,S group	RTS,S/AS01 _E	IM	Deltoid	Left
Visit 4	0.5 ml	Coad group	RTS,S/AS01 _E	IM	Deltoid	Left
	0.5 ml	Coad group	Yellow fever	IM	Anterolateral thigh	Right
	0.5 ml	Coad group	Measles and Rubella	SC	Anterolateral thigh	Left
	0.5 ml	RTS,S group	RTS,S/AS01 _E	IM	Deltoid	Left
	0.5 ml	Control group	Yellow fever	IM	Anterolateral thigh	Right
	0.5 ml	Control group	Measles and Rubella	SC	Anterolateral thigh	Left
Visit 6	0.5 ml	RTS,S group	Yellow fever	IM	Anterolateral thigh	Right
	0.5 ml	RTS,S group	Measles and Rubella	SC	Anterolateral thigh	Left
	0.5 ml	Control group	RTS,S/AS01 _E	IM	Deltoid	Left
Visit 7	0.5 ml	Control group	RTS,S/AS01 _E	IM	Deltoid	Left
Visit 8	0.5 ml	Control group	RTS,S/AS01 _E	IM	Deltoid	Left
Visit 10	0.5 ml	Coad group	RTS,S/AS01 _E	IM	Deltoid	Left
	0.5 ml	RTS,S group	RTS,S/AS01 _E	IM	Deltoid	Left
Visit 12	0.5 ml	Control group	RTS,S/AS01 _E	IM	Deltoid	Left

¹ IM: Intramuscular; O: Oral; SC: Subcutaneous

The subjects will be observed closely for at least 60 minutes following the administration of the vaccines, with appropriate medical treatment readily available in case of anaphylaxis.

6.3.1. RTS,S/AS01_E (0.5 ml dose)

The commercial presentation will be a two-doses glass vial of lyophilized RTS,S antigen to be reconstituted with a two-doses glass vial of AS01_E Adjuvant System. The final product for administration will be prepared by reconstitution of the lyophilized antigen with the liquid adjuvant to deliver two doses (1.0 ml). A single dose consists of 0.5 ml of RTS,S/AS01_E final preparation. All vials of vaccine provided in this study are intended for single use only.

Disinfect top of vaccine vial (pellet) and adjuvant vial with alcohol swabs and let dry. Withdraw the contents of the adjuvant vial in a syringe and inject adjuvant into the vial of lyophilized antigen. The pellet is then dissolved by gently shaking the vial. Wait for one minute to ensure complete dissolution of vial contents before withdrawing one dose of RTS,S/AS01_E (0.5 ml). The reconstituted vaccine should be administered by slow IM

injection, using a fresh 25G needle with length of one inch (25 mm), in the left deltoid. Vaccine should be injected within four hours of reconstitution (storage at +2°C to +8°C).

6.3.2. Combined measles and rubella vaccine (MR-VAC) (0.5 ml dose)

The combined measles and rubella vaccine will be used according to manufacturer instructions and the Summary of Product Characteristics. The vaccine will be administered as a SC injection into the left anterolateral thigh.

6.3.3. Licensed WHO prequalified yellow fever vaccine (0.5 ml dose)

The YF vaccine will be used according to manufacturer instructions and the Summary of Product Characteristics. The vaccine will be administered as an IM injection into the right anterolateral thigh.

6.3.4. Vitamin A (100000 IU dose)

The Vitamin A will be used according to manufacturer instructions and the Summary of Product Characteristics. Vitamin A will be administered orally.

6.4. Replacement of unusable vaccine/product doses

In addition to the vaccine/product doses provided for the planned number of subjects (including over-randomization when applicable), at least 10% additional vaccine/product doses will be supplied to replace those that are unusable.

6.5. Contraindications to subsequent vaccination

The following events constitute absolute contraindications to further administration of study vaccines. If any of these events occur during the study, the subject must not receive additional doses of vaccines but may continue other study procedures at the discretion of the investigator (see Section 8.4).

- Anaphylaxis following the administration of vaccines.
- Any confirmed or suspected immunosuppressive or immunodeficient condition, including human immunodeficiency virus (HIV) infection.
- Any condition that in the judgment of the investigator would make intramuscular injection unsafe.
- Failure to thrive.
- Any other findings that the investigator feels would increase the risk of having an adverse outcome from participation in the trial.
- Administration of a dose of measles, rubella or YF vaccines outside of this study protocol.

The following events constitute contraindications to administration of study vaccines at that point in time; if any of these events occur at the time scheduled for vaccination, the subject may be vaccinated at a later date, within the time window specified in the

protocol (see Section 5.5), or the subject may be withdrawn at the discretion of the investigator (see Section 8.4).

- Acute disease and/or fever at the time of vaccination.
 - Fever is defined as temperature $\geq 37.5^{\circ}\text{C}/99.5^{\circ}\text{F}$ for oral, axillary or tympanic route, or $\geq 38.0^{\circ}\text{C}/100.4^{\circ}\text{F}$ for rectal route. The preferred route for recording temperature in this study will be axillary.
 - Subjects with a minor illness (such as mild diarrhea, mild upper respiratory infection) without fever can be administered all vaccines/.
- A lesion that would prevent injection.
- Administration of a vaccine not foreseen by the study protocol within seven days of any dose of RTS,S/AS01_E, YF vaccine and the combined measles and rubella vaccine.

6.6. **Warnings and precautions**

Refer to the approved product label/package insert.

6.7. **Concomitant medications/products and concomitant vaccinations**

At each study visit/contact, the investigator should question the subject's parent(s)/LAR(s) about any medications/products taken and vaccinations received by the subject.

6.7.1. **Recording of concomitant medications/products and concomitant vaccinations**

The following concomitant medication(s)/product(s)/vaccine(s) must be recorded in the eCRF.

- Anti-inflammatory, analgesics, anti-pyretic, and systemic antibiotics administered starting 30 days before and following each dose of study vaccine.
- Any concomitant vaccination administered in the period starting seven days before the first dose of study vaccine and ending at Visit 5 (Month 4).
- Prophylactic medication (i.e. medication administered in the absence of ANY symptom and in anticipation of a reaction to the vaccination).

E.g. an anti-pyretic is considered to be prophylactic when it is given in the absence of fever and any other symptom, to prevent fever from occurring (fever is defined as temperature $\geq 37.5^{\circ}\text{C}/99.5^{\circ}\text{F}$ for oral, axillary or tympanic route, or $\geq 38.0^{\circ}\text{C}/100.4^{\circ}\text{F}$ for rectal route).

- Any concomitant medications/products/vaccines listed in Section 6.7.2.
- Any concomitant medication/product/vaccine relevant to a SAE* or administered at any time during the study period for the treatment of a SAE*.

* SAEs that are required to be reported per protocol.

- Any concomitant medications/products/vaccines relevant to a SAE/pIMD to be reported as per protocol or administered at any time during the study period for the treatment of a SAE/pIMD. In addition, concomitant medications relevant to SAEs and pIMD need to be recorded on the expedited Adverse Event report.

6.7.2. Concomitant medications/products/vaccines that may lead to the elimination of a subject from ATP analyses

The use of the following concomitant medications/products/vaccines will not require withdrawal of the subject from the study but may determine a subject's evaluability in the ATP analysis. See Section 10.5 for cohorts to be analyzed.

- Use of a drug or vaccine that is not approved for that indication (by one of the following regulatory authorities: FDA or European Union member state or WHO [with respect to prequalification]) other than the study vaccines during the study period.
- Immunosuppressants or other immune-modifying drugs administered chronically (i.e. more than 14 days) during the study period. For corticosteroids, this will mean prednisone ≥ 0.5 mg/kg/day or equivalent. Inhaled and topical steroids are allowed.
- A vaccine not foreseen by the study protocol administered during the period starting from seven days before each dose of vaccine(s) and ending 42 days after.*

* In case an emergency mass vaccination for an unforeseen public health threat (e.g.: a pandemic or polio control) is organized by the public health authorities, outside the routine immunization program, the time period described above can be reduced if necessary for that vaccine provided it is licensed and used according to its Summary of Product Characteristics or Prescribing Information and according to the local governmental recommendations and provided a written approval of the Sponsor is obtained.

- Immunoglobulins and/or any blood products administered during the study period.
- Administration of a dose of measles, rubella or YF vaccines from seven days before the first dose of study vaccine and ending at the first birthday of the subject.

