5.6.9. Check contraindications, warnings and precautions to vaccination

Contraindications, warnings and precautions to vaccination must be checked at the beginning of each vaccination visit. Refer to Sections [6.5](#) and [6.6](#) for more details.

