5.6.10. Assess pre-vaccination body temperature

The axillary, rectal, oral or tympanic body temperature of all subjects needs to be measured prior to any study vaccine/ product administration. The preferred route for recording temperature in this study will be axillary. If the subject has fever [fever is defined as temperature $\geq 37.5^{\circ}\text{C}/99.5^{\circ}\text{F}$ for oral, axillary or tympanic route, or $\geq 38.0^{\circ}\text{C}/100.4^{\circ}\text{F}$ for rectal route] on the day of vaccination, the vaccination visit will be rescheduled within the allowed interval for this visit (see [Table 7](#)).

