5.6.11. Study Vaccines/product administration

- After completing all prerequisite procedures prior to vaccination, study vaccines will be administered (refer to Section [6.3](#) for detailed description of the vaccines/product administration procedure). If the investigator or delegate determines that the subject's health on the day of administration temporarily precludes vaccines/product administration, the visit will be rescheduled within the allowed interval for this visit (refer to [Table 7](#)).
- The subjects will be observed closely for at least 60 minutes following the administration of the vaccines, with appropriate medical treatment readily available in case of anaphylaxis.
- Vaccination will take place at the vaccination center. All vaccinations will be given by a qualified person: a nurse or a doctor. A staff member experienced in the resuscitation of children will be available at all vaccination sessions.

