 - For the Control group, the occurrence of solicited general AEs over a 7-day follow-up period (day of administration and 6 subsequent days) after administration of Vitamin A at 6 months of age (Visit 2).
 - For the Coad and the RTS,S groups, the occurrence of solicited local and general AEs over a 7-day follow-up period (day of vaccination and 6 subsequent days) after dose of study vaccines administered at 7.5 months of age (Visit 3).
 - For the Control group, the occurrence of solicited general AEs over a 7-day follow-up period (day of visit and 6 subsequent days) after Visit 3 (7.5 months of age).
 - For all groups, the occurrence of solicited general and local AEs over a 14-day follow-up period (day of vaccination and 13 subsequent days) after dose of study vaccines administered at 9 months of age (Visit 4).
- Unsolicited AEs.
 - For all groups, the occurrence of unsolicited AEs over a 30-day follow-up period (day of administration and 29 subsequent days) after administration of Vitamin A and study vaccines at 6 months of age (Visit 2).
 - For the Coad and the RTS,S groups, the occurrence of unsolicited AEs over a 30-day follow-up period (day of vaccination and 29 subsequent days) after dose of study vaccines administered at 7.5 months of age (Visit 3).
 - For the Control group, the occurrence of unsolicited AEs over a 30-day follow-up period (day of visit and 29 subsequent days) after Visit 3 (7.5 months of age).
 - For all groups, the occurrence of unsolicited AEs over a 42-day follow-up period (day of vaccination and 41 subsequent days) after dose of study vaccines administered at 9 months of age (Visit 4).

- For the Coad and the RTS,S groups, the occurrence of unsolicited AEs over a 30-day follow-up period (day of vaccination and 29 subsequent days) after the booster dose of study vaccine administered at 27 months of age (Visit 10).
- For the Control group, the occurrence of unsolicited AEs over a 30-day follow-up period (day of vaccination and 29 subsequent days) after dose of study vaccines administered at 10.5, 11.5, 12.5 and 30 months of age (Visit 6, 7, 8 and 12).
- SAEs: all, fatal and related SAEs.
 - The occurrence of SAEs occurring within 30 days (day of vaccination and 29 subsequent days) after each administrations.
 - The occurrence of SAEs from Screening visit (Visit 1) until Month 4.5.
 - The occurrence of SAEs from Screening visit (Visit 1) until study end (Month 33 for Coad and RTS,S groups and Month 36 for the Control group).

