11.2.5. Safety

- For a given subject and the analysis of solicited symptoms, missing or non-evaluable measurements will not be replaced. Therefore the analysis of the solicited symptoms based on the Exposed Set will include only vaccinated subjects for doses with documented safety data (i.e., symptom screen completed). More specifically the following rules will be used:
 - Subjects who documented the absence of a solicited symptom after one dose will be considered not having that symptom after that dose.
 - Subjects who documented the presence of a solicited symptom and fully or partially recorded daily measurement over the solicited period will be included in the summaries at that dose and classified according to their maximum observed daily recording over the solicited period.
 - Subjects who documented the presence of a solicited symptom after one dose without having recorded any daily measurement will be assigned to the lowest intensity category at that dose (i.e., 37.5°C for fever or grade 1 for other symptoms).
 - Doses without symptom sheets documented will be excluded.
- For analysis of unsolicited adverse events, such as serious adverse events or adverse events by primary MedDRA term, and for the analysis of concomitant medications, all vaccinated subjects (or receiving Vitamin A) will be considered. Subjects who did not report the event or the concomitant medication will be considered as subjects without the event or the concomitant medication respectively.
- The maximum intensity of local injection site redness/swelling will be coded as follows:

Grade	Redness/swelling
0	Absent
1	> 0 mm and < 5 mm
2	≥ 5 mm and ≤ 20 mm
3	> 20 mm

- For the analysis, temperatures will be coded as follows:

Grade	Temperature
0	< 37.5°C
1	≥ 37.5°C - ≤ 38.0°C
2	> 38.0°C - ≤ 39.0°C
3	> 39.0°C

Note that for all tables described in this section, the way the percentage of subjects will be derived will depend on the event analysed (see table below for details). As a result, the N value will differ from one table to another.

Event	N used for deriving % per subject for Vaccination phase	N used for deriving % per dose for Vaccination phase
Concomitant vaccination	All subjects with study vaccine administered	All study visits with study vaccine administered

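### No rule defers a Control child who is febrile at Visit 3, so the Control fever rate beside RTS,S Dose 2 can be inflated and the descriptive excess over Control understated

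*Protocol*

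**What the plan says.** Three protocol passages deal with a child who is unwell on the day.

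- Section 5.6.10: if the child has fever (37.5°C or more by the preferred axillary route) "on the day of vaccination, the vaccination visit will be rescheduled within the allowed interval for this visit".
- Section 5.6.11: if the child's health "temporarily precludes vaccines/product administration, the visit will be rescheduled within the allowed interval for this visit".
- Section 6.5: the temporary contraindications include "Acute disease and/or fever at the time of vaccination", and "if any of these events occur at the time scheduled for vaccination, the subject may be vaccinated at a later date"; withdrawal is the stated alternative. It adds a limit: "Subjects with a minor illness (such as mild diarrhea, mild upper respiratory infection) without fever can be administered all vaccines".

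Under Section 5.6.9 contraindications "must be checked at the beginning of each vaccination visit".

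Table 12 has no Control entry at Visit 3. Table 6, the Control schedule, shows no contraindication check before Visit 4. It does appear to mark a temperature at Visit 3.

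Follow-up of Control at Visit 3 is nevertheless an endpoint in Section 10.2: "For the Control group, the occurrence of solicited general AEs over a 7-day follow-up period (day of visit and 6 subsequent days) after Visit 3". SAP 11.2.5 has a child with a symptom "classified according to their maximum observed daily recording over the solicited period". SAP Templates 26, 28 and 34 place Control general symptoms at Dose 2 next to Coad and RTS,S, and Template 36 does the same for maximum temperature by dose.

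**The concern.** Coad and RTS,S children start the 7 days after Visit 3 only once they have passed the deferral rules. No rule sets the same condition for Control. The fever threshold for deferral is also the threshold for the solicited event, and the visit day is inside the window. A Control child febrile on arrival is thus an event by definition, while the same child in another group would be seen later, when well.

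The problem is specific to Visit 3. At Visit 2 the exclusion criterion for acute disease or fever at enrolment covers every group, and at Visit 4 every group is vaccinated. Control after Visit 3 is the only concurrent unvaccinated comparator for RTS,S Dose 2 at 7.5 months. What is at stake is how much of the general reaction, chiefly fever, a reader will credit to that dose when comparing columns.

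**Working it through.** **Denominator.** Protocol Section 10.4 gives 205 evaluable per group and about 12% loss: 205/0.88 = 232.95, so 233, as stated. No fever rate, and no share of children febrile at Visit 3, appears in either document. Every rate below is an assumption.

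**Model.** Let p be the share of children febrile at the scheduled visit, b the 7-day fever risk in a child well at the visit, and r the 7-day fever rate after RTS,S Dose 2.

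- Control as tabulated, with no deferral: p + (1−p)b.
- Background carried by Coad and RTS,S, with deferral: b.
- Inflation: p + (1−p)b − b = p(1−b).
- 95% CI half-width for the difference, with c the tabulated Control rate: 1.96 × √[c(1−c)/233 + r(1−r)/233].

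**One case in full** (p = 5%, b = 5%, r = 20%). c = 0.05 + 0.95 × 0.05 = 0.0975, so the inflation is 4.75 points. The true difference is 15.0 points and the tabulated one 20 − 9.75 = 10.25. The half-width is 1.96 × √[(0.0880 + 0.1600)/233] = 6.4 points.

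**Range of p, with b = 5% and r = 20%** (true difference 15.0 points):

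| p | Inflation (points) | Tabulated difference (points) | CI half-width (points) |
|---|---|---|---|
| 0.5% | 0.5 | 14.5 | 5.9 |
| 1% | 0.95 | 14.05 | 6.0 |
| 2% | 1.9 | 13.1 | 6.1 |
| 5% | 4.75 | 10.25 | 6.4 |
| 10% | 9.5 | 5.5 | 6.8 |

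**Range of b.** For b from 2% to 20%, the inflation is 1.6 to 2.0 points at p = 2%, 4.0 to 4.9 at p = 5%, and 8.0 to 9.8 at p = 10%. Over p = 0.5% to 10% the whole span is 0.4 to 9.8 points. For p up to 2% it stays below the half-width of 4.3 to 7.9 points (r = 10% to 30%).

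**Illness without fever.** If a deferred child has only a chance f of fever in the 7 days, the inflation is p(f−b). With p = 5%, f = 20% and b = 5% it is 0.75 points. The point therefore rests on fever at the visit.

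**Coad against RTS,S.** Both groups follow the same rules at Visit 3, so the term cancels.

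**What is recorded.** In the extracted Table 6 the Control temperature row has three marks before Visit 6. They start in the same column as the single Vitamin A mark, which belongs to Visit 2, so they most likely stand for Visits 2, 3 and 4. Because the columns are displaced, this needs checking against the source table. Physical examination at Visit 3 does not require an eCRF entry, and Section 5.6.5 has its findings recorded at Visit 1 only. Acute disease at Visit 3 is therefore not clearly available for Control; temperature probably is.

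**Dose numbering.** SAP 11.2.2 numbers doses by visits at which vaccination occurred, and SAP 11.2.5 limits per-dose denominators to visits with study vaccine given. Control Visit 3 meets neither condition. The templates nonetheless carry a Control Dose 2 row, with local symptoms not applicable, which can only be Visit 3.

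**The case against.** The safety objective compares Coad with RTS,S given alone. Control is not named in it, other comparisons are descriptive, and attribution does not rest on Control alone: Template 34 has separate rows for related symptoms, and Template 30 marks Control as not applicable at Doses 1 and 2. This stands, and it confines the problem to the descriptive excess over Control. A reader might infer that the reported reaction to RTS,S Dose 2 is itself too low; it is not, because the Coad and RTS,S rates do not depend on Control.

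A reader might also infer that febrile Control children are in fact seen and counted on the day. The documents do not say so. Nothing forbids moving the visit, the Visit 3 window spans ages 7 and 8 months, and the apparent temperature mark would fit parallel handling. But nothing requires it either, and unrecorded site discretion would leave the starting state unknown.

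Extending the point to acute illness generally goes too far, because Section 6.5 allows vaccination during minor illness without fever. Nor can it be said that the Control per-dose overall rows are affected: under SAP 11.2.5 Visit 3 should not enter their denominator.

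Finally, restricting Control outright would remove children whose deferred counterparts return and are counted in the other groups. That argues against replacing the main row, not against a supplementary one.

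**Conclusion.** The asymmetry is in the text. Followed as written, the plan biases the descriptive RTS,S-minus-Control contrast after Visit 3 towards a smaller vaccine reaction, by about p(1−b). That is about 2 points or less, within sampling error, if no more than 2% of children are febrile at the visit, and 4 points or more at 5% or above. The size rests on two rates that the documents do not give, and on febrile Control children not being deferred in practice. A larger sample would not remove it. Neither the safety objective nor the Dose 2 rates in Coad and RTS,S change. This is a cheap improvement to the safety tables and does not threaten the trial's conclusions.

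**What to change.** 1. In SAP 6.5.1 and Templates 26, 28, 34 and 36, keep the Control Visit 3 row for all children on the Exposed Set. Add a supplementary Control row restricted to children below 37.5°C axillary at the Visit 3 temperature, once it is confirmed that Table 6 records one. Leave the Control overall-per-subject rows unrestricted.
2. Reconcile protocol Sections 5.6.10, 5.6.11 and 6.5 and Table 6 on what applies to Control at Visit 3. The statistical requirement is only that the 7-day observation starts from the same state in all groups.
3. Reconcile SAP 11.2.2 and 11.2.5 with the templates on whether Control Visit 3 counts as Dose 2 and in which denominators it belongs.

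The cost is SAP wording, one extra row and a filter on a temperature that appears to be collected already. The downside is that the restricted row omits a few Control children (about 5 of 233 at p = 2%, about 12 at 5%) whose deferred counterparts remain in the other groups, so it should be read beside the all-children row.
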